#### **4.3.3.1 Potential drug-induced liver injury IMP discontinuation criteria**

Subjects with potential drug-induced liver injury (PDILI) must be assessed to determine if IMP must be immediately and permanently discontinued. In addition, all concomitant medications and herbal supplements that are not medically necessary should also be discontinued.

The PDILI criteria below require immediate and permanent discontinuation of IMP:

- Subjects with either of the following:
  - ALT or AST  $\geq 5\times$ ULN
  - ALT or AST  $\geq 3\times$ ULN and coexisting total bilirubin  $\geq 2\times$ ULN
- Subjects with ALT or AST  $\geq 3\times$ ULN who exhibit temporally associated symptoms of hepatitis or hypersensitivity. Hepatitis symptoms include fatigue, nausea, vomiting, and right upper quadrant pain or tenderness. Hypersensitivity symptoms include fever (without clear alternative cause), rash, or eosinophilia (ie,  $>5\%$ ).

The PDILI criterion below requires discussion with the Medical Monitor to decide whether the subject is allowed to continue on IMP.

- Subjects with ALT or AST  $\geq 3\times$ ULN (and  $\geq 2\times$  Baseline) and  $<5\times$ ULN, total bilirubin  $<2\times$ ULN, and no eosinophilia (ie,  $\leq 5\%$ ), with no fever, rash, or symptoms of hepatitis (eg, fatigue, nausea, vomiting, right upper quadrant pain or tenderness).

Evaluation of PDILI must be initiated as described in [Section 8.3.2](#). If subjects are unable to comply with the applicable monitoring schedule, IMP must be discontinued immediately.

Investigators should attempt to obtain information on subjects in the case of IMP discontinuation to complete the final evaluation. Subjects with PDILI should not be withdrawn from the study until investigation and monitoring are complete. All results of these evaluations and observations, as well as the reason(s) for IMP discontinuation and subject withdrawal (if applicable), must be recorded in the source documents. The eCRF must document the primary reason for IMP discontinuation.

## 4.4 Study treatments

### 4.4.1 Treatments to be administered

#### 4.4.1.1 Subjects enrolling from SP847 or other LCM pediatric clinical studies in epilepsy

Subjects who have participated in SP847 (or other LCM pediatric clinical studies in epilepsy), who are eligible to participate in the open-label study SP848, and who choose to enter SP848, will begin SP848 on the LCM dose they achieved in the primary study.

Subjects who enroll from EP0060 will begin SP848 with an equivalent dose to the last dose they received in EP0060; however, the LCM dose may be further titrated/adjusted to a level to optimize tolerability and seizure control (up to a maximum level as described in [Section 4.4.1.3](#)). For those subjects who initiated adjunctive LCM treatment in EP0060, the recommended LCM dose titration approach is outlined in Section [4.4.1.2](#).

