12. For all subjects  $\geq 6$  years of age, regardless of whether or not a C-SSRS was completed at Screening, subject has actual suicidal ideation as indicated by a positive response ("Yes") to either Question 4 or Question 5 of the "since last visit" version of the C-SSRS. The subject should be referred immediately to a Mental Healthcare Professional and must be withdrawn from the study.

Participation in this study **may** be discontinued for any of the following reasons:

1. Any clinically relevant change in medical or psychiatric condition (if in the opinion of the investigator, the condition warrants discontinuation from the study).
2. Subject requires a medication that is not permitted by the protocol.
3. Subject and/or delegated caregiver is unable to manage the completion of the diary or is noncompliant with study procedures or medication, in the opinion of the investigator.
5. For subject who did not complete a C-SSRS at Screening, subject had actual suicidal ideation in the past 6 months as indicated by a positive response ("Yes") to either Question 4 or Question 5 of the screening version of the C-SSRS. The investigator must immediately refer the subject to a Mental Healthcare Professional and use clinical judgment as to whether to withdraw the patient from the study.

If a subject from SP848 enrolls in EP0060 and either withdraws consent solely due to route of LCM administration (iv) or if the subject requires more than 10 iv LCM infusions, the subject may be allowed to return to SP848 after discussion with and agreement from the Medical Monitor. If a subject from SP848 is advised to withdraw from the SP848 after participation in EP0060, the subject will be required to return to the SP848 to complete the required ETV and Safety Follow-up assessments.

Investigators should attempt to obtain information on subjects in the case of withdrawal. For subjects considered as lost to follow up, the investigator should make efforts (at least 1 phone call and 1 written message to the subject), and document his/her efforts (date and summary of the phone call and copy of the written message in the source documents), to complete the final evaluation. All results of these evaluations and observations, together with a narrative description of the reason(s) for removing the subject, must be recorded in the source documents. The eCRF must document the primary reason for withdrawal.

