**4.4.1.3 All subjects**

The investigator, together with the subject/caregiver (including parent/legal guardian), will be able to choose either the oral solution (syrup) formulation or the tablet formulation of LCM in this study. The study medication will be orally administered bid (at 12-hour intervals, once in the morning and once in the evening) in equally divided doses. The oral solution (syrup) formulation will be measured and orally administered via a dosing syringe. The selection of doses, titration scheme, and rate of taper in SP847 were based on adult studies and were adjusted to a mg/kg basis plus 40% (ie, 600mg/day adult dose of LCM corresponds to  $[600\text{mg}/70\text{kg}] \times 1.4 =$  approximately 12mg/kg/day for a child). The selection of doses in this trial is based on the maximum recommended dose in SP847.

The investigator may adjust the LCM dose to a minimum of 2mg/kg/day (oral solution [syrup]) or 100mg/day (tablet) and a maximum of 12mg/kg/day (oral solution [syrup] or the corresponding dose levels for the tablet formulation) not to exceed 600mg/day based on body weight, even if the subject's body weight exceeds 50kg. The maximum permitted LCM dose in SP848 is 12mg/kg/day or 600mg/day, whichever is lower.

The investigator may increase the dose of LCM no faster than 2mg/kg/day (oral solution [syrup]) or 100mg/day (tablet) per week to a maximum of 12mg/kg/day (oral solution [syrup] or the corresponding dose levels for the tablet formulation) not to exceed 600mg/day based on body weight, even if the subject's body weight exceeds 50kg. The maximum permitted LCM dose in SP848 is 12mg/kg/day or 600mg/day, whichever is lower. The investigator may decrease the dose of LCM to a minimum of 2mg/kg/day (oral solution [syrup] or the corresponding dose level for the tablet formulation). Increases in the LCM dose must occur only during office visits. It should be noted, in cases of incomplete doses (eg, subject spits out all or a portion of the syrup), missed doses, or administration of an erroneous volume of syrup, study medication should not be readministered and these subjects would remain at their assigned dose.

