## **5.2 Titration Visit(s) (TV1, TV2, TV3, TV4, TV5, TV6)**

Eligible subjects who enter directly into SP848 (without prior participation in SP847 or another applicable LCM primary study) will initiate treatment with LCM at TV1, and the LCM dose will be titrated over the following week(s). Titration Visits are not applicable for subjects who have participated in SP847 or another LCM primary study; the first visit in SP848 for these subjects is Visit 1 (see Section 5.3).

At TV1, subjects who have enrolled directly into SP848 will receive a single dose of LCM (1mg/kg [oral solution] or 50mg [tablet]) during the clinic visit. Over the following days, subjects will be administered LCM 1mg/kg bid (oral solution) or LCM 50mg bid (tablet), and will begin titrating in weekly increments of 2mg/kg/day (oral solution) or 100mg/day (tablet) up to a level to optimize tolerability and seizure control (not to exceed 12mg/kg/day [or 600mg/day based on body weight, whichever is lower]). Subjects must be on each LCM dose for at least 5 days before titrating up to the next dose. It should be noted, in cases of incomplete doses (eg, subject spits out all or a portion of the syrup), missed doses, or administration of an erroneous volume of syrup, study medication should not be readministered and these cases would not be considered dose reductions. The LCM dose titration steps are summarized in Section 4.4.1.2.

A total of up to 6 Titration Visits may be required (eg, for a subject whose dose is titrated to the maximum permitted dose of LCM 12mg/kg/day). However, based on tolerability and seizure control, a subject's LCM dose may be titrated to a lower dose level; in such a case, fewer than 6 Titration Visits would be required.

The following assessments are required for each TV:

- Concomitant medications assessment
- Concomitant AEDs assessment
- Brief physical examination
- Brief neurological examination
- 12-lead ECG (2 interpretable recordings approximately 20 to 30 minutes apart prior to vital signs assessment and collection of any blood samples)

- Vital signs assessment (blood pressure and pulse)
- Body weight
- Blood sample for clinical chemistry, hematology, and endocrinology (TV4 only)
- Urine sample for urinalysis (TV4 only)
- LCM return/compliance (as applicable)
- Subject diary assessment
- C-SSRS
- Adverse event reporting
- Health care resource use
- Dispense subject diary
- Dispense LCM (as applicable)

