### 5.3 Visit 1 (Week 0)

For subjects who completed SP847, Visit 1 for SP848 was the same as Day 2 of the second PK collection time period (which may include an overnight stay at a hospital or medical facility) in SP847 (Day 28 for Cohorts 1, 2, 3, and 5 with maximum recommended dose of 8mg/kg/day; Day 35 for Cohorts 2 to 5 with maximum recommended dose of 10mg/kg/day; and Day 42 for Cohorts 2 to 5 with maximum recommended dose of 12mg/kg/day). For subjects who discontinued SP847 due to a dose reduction or status epilepticus, Visit 1 was the Early Termination Visit in SP847. For subjects in SP847 who were titrated up to the maximum permitted dose of 600mg/day sooner than the study schedule would ordinarily indicate (based on body weight) and who enroll in SP848, the Early Termination Visit of SP847 also served as Visit 1 for SP848.

For subjects who enroll in SP848 after participation in other LCM pediatric clinical studies besides SP847 (ie, SP0966 and EP0060) in epilepsy, SP848 Visit 1 will be specified in the respective primary study protocol.

For subjects who enter directly into SP848 (without prior participation in SP847 or other LCM pediatric clinic studies in epilepsy), the LCM dose will be titrated at weekly intervals as described in Section 4.4.1.2 and Section 5.2. These subjects will reach Visit 1 either (1) when the LCM dose is titrated to a level that, in the opinion of the investigator, optimizes tolerability and seizure control, or (2) when the maximum permitted LCM dose is reached (12mg/kg/day [or 600mg/day based on body weight, whichever is lower]). In the case of a subject who requires a dose reduction during the Titration Visits, the subject's LCM dose will be returned to the

previous dose level and the next clinic visit will be Visit 1 at the reduced level. Visit 1 should occur at least 5 days after the final TV. At Visit 1, the progress in SP848 for subjects who entered directly into SP848 and for subjects who have enrolled from SP847 or other LCM pediatric clinical studies in epilepsy will be aligned; subsequent regularly scheduled clinic visits for all subjects will be at 4-week intervals as outlined in the following sections.

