## 5.18 Unscheduled Visit(s)

An Unscheduled Visit may be performed at the investigator's discretion. If the LCM dose is decreased between scheduled clinic visits due to an AE, if an LCM dose increase is required at any time, or if a new concomitant AED is introduced, the subject must return for an Unscheduled Visit. If an AE prompts a dose reduction, the reduction can be implemented immediately at the investigator's discretion. However, the subject should return to the clinic as soon as possible for an Unscheduled Visit.

The following assessments are required:

- Concomitant medications assessment
- Concomitant AEDs assessment
- Brief physical examination
- Brief neurological examination

- 12-lead ECG (2 interpretable recordings approximately 20 to 30 minutes apart prior to vital signs assessment and collection of any blood samples)
- Vital signs assessment (blood pressure and pulse)
- Body weight
- LCM return/compliance (as applicable)
- Subject diary assessment
- C-SSRS (only if Unscheduled Visit is conducted due to an AE)
- Adverse event reporting
- Health care resource use
- Dispense LCM (as applicable)
- If possible, a blood sample for LCM and concomitant AED plasma concentrations (at any time post-dosing with LCM) if the unscheduled visit is due to a SAE

Additional assessments can be performed at the investigator's discretion.

All subjects will be required to have an ECG (2 interpretable recordings) conducted at LCM  $C_{max}$  1 week after an initial LCM dose increase to a LCM dose level that is  $\geq 8\text{mg/kg/day}$  or after a new concomitant AED is introduced. This ECG can be conducted at an Unscheduled Visit, if necessary. Subjects having a LCM dose increase to  $\geq 8\text{mg/kg/day}$  will be required to arrive at the clinic prior to taking their morning dose of LCM. Subjects will be administered their morning LCM dose by study personnel at the clinic so that an ECG (2 interpretable recordings approximately 20 to 30 minutes apart prior to vital signs assessment) can be performed 30 minutes to 1 hour after the administration of LCM (ie, at LCM steady state  $C_{max}$ ).

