- n Lacosamide for taper will be dispensed only for subjects who achieve a dose of LCM  $\geq 6\text{mg/kg/day}$  (oral solution [syrup]) or  $\geq 300\text{mg/day}$  (tablet). It is recommended that the LCM dose be tapered gradually in weekly decrements of  $4\text{mg/kg/day}$  (oral solution [syrup]) or  $200\text{mg/day}$  (tablet). A slower taper of  $2\text{mg/kg/day}$  (oral solution [syrup]) or  $100\text{mg/day}$  (tablet) is permitted, if medically necessary. In case of an emergency, a faster taper is permitted after discussion with the medical monitor, whenever possible.
- o As applicable.
- p For all subjects  $\geq 6$  years of age already enrolled, the “already enrolled” version should be completed at the next clinic visit, and the “since last visit” version should be completed thereafter.
- q The C-SSRS assessment should be completed if the Unscheduled Visit is due to an AE.
- r Ongoing AEs from the primary study will be followed, as well as recording of new AEs during the current study.

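### Children aged 6 or over who started LCM in EP0060 may follow the direct enrollees' weekly titration steps with a required C-SSRS only about every 28 days instead of about every 7, so detection of withdrawal criterion 12 can be delayed

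*Protocol*

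**What the plan says.** **Titration.** A subject entering from EP0060 begins SP848 on a dose equivalent to the last EP0060 dose and may be titrated further (Section 4.4.1.1). The same section adds: "For those subjects who initiated adjunctive LCM treatment in EP0060, the recommended LCM dose titration approach is outlined in Section" 4.4.1.2. The steps there are 2mg/kg/day (oral solution) or 100mg/day (tablet) per week, up to 12mg/kg/day or 600mg/day, whichever is lower.

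**Visits.** Section 5.2 says: "Titration Visits are not applicable for subjects who have participated in SP847 or another LCM primary study". Section 5.3 names EP0060 among those studies, so these children start at Visit 1. Direct enrollees reach Visit 1 only "when the LCM dose is titrated to a level that, in the opinion of the investigator, optimizes tolerability and seizure control", or at the maximum permitted dose. Before that they have a C-SSRS at every Titration Visit (Section 5.2, Table 16-3).

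**Dose increases.** Section 4.4.1.3: "Increases in the LCM dose must occur only during office visits". Section 5.18 requires an Unscheduled Visit "if an LCM dose increase is required at any time", and Table 16-1 footnote e says the same of increases between scheduled visits.

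**C-SSRS at Unscheduled Visits.** Table 16-1 footnote q: "The C-SSRS assessment should be completed if the Unscheduled Visit is due to an AE". Section 5.18 and Table 16-2 footnote o carry the same condition.

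**Consequence of a positive answer.** Under mandatory withdrawal criterion 12 (Section 4.3.3), for a child aged 6 or over who answers Yes to Question 4 or 5 of the Since Last Visit form: "The subject should be referred immediately to a Mental Healthcare Professional and must be withdrawn from the study".

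**The concern.** For initial titration the protocol sets its own standard: in direct enrollees aged 6 or over, each weekly step comes with a C-SSRS. EP0060 initiators may follow the same steps, but without the visits that carry the questionnaire. Most of their increases can fall at Unscheduled Visits, where a dose increase does not by itself trigger a C-SSRS. The protocol gives no reason for the difference.

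Criterion 12 is defined by the instrument. A clinical impression may prompt the C-SSRS, but only the answer to Question 4 or 5 meets the criterion. At stake is how soon a child with active suicidal ideation is found and referred, when the protocol asks for immediate referral. Sample size and error rates are not affected.

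**Working it through.** The protocol gives no figure to reproduce. The check sets the weekly steps against the visits at which a C-SSRS is required.

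**Inputs**
- Step: 2mg/kg/day per week, maximum 12mg/kg/day (Sections 4.4.1.2 and 4.4.1.3). The tablet scale, 100 to 600mg/day in 100mg/day steps, gives the same counts.
- Entry dose *d*: not stated, so a range is shown.
- Visits with a required C-SSRS after entry from EP0060: Weeks 0, 4 and 8 (Sections 5.3, 5.5 and 5.6). The Week 0 result may be taken from the last EP0060 assessment.
- Visit window: 7 days either way, relative to Visit 1 (Section 5).

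**Steps off the schedule.** The number of increases is n = (12 − d)/2. On nominal dates:

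| Entry dose (mg/kg/day) | n | Off-schedule, first increase at Week 1 | Off-schedule, first increase at Visit 1 |
|---|---|---|---|
| 2 | 5 | 4 of 5 (Weeks 1, 2, 3, 5) | 3 of 5 (Weeks 1, 2, 3) |
| 4 | 4 | 3 of 4 (Weeks 1, 2, 3) | 3 of 4 (Weeks 1, 2, 3) |
| 6 | 3 | 3 of 3 (Weeks 1, 2, 3) | 2 of 3 (Weeks 1, 2) |
| 8 | 2 | 2 of 2 (Weeks 1, 2) | 1 of 2 (Week 1) |
| 10 | 1 | 1 of 1 (Week 1) | 0 of 1 |
| 12 | 0 | none | none |

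**Dose reached before the Week 4 form.** With a first increase at Week 1, three steps precede it, so the dose is d + 3 × 2: from 2 to 8, from 4 to 10, from 6 to 12mg/kg/day. A direct enrollee moves one step, 2mg/kg/day, between consecutive forms.

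**Effect of the window.** Visit 2 can fall on day 28 − 7 = 21 to day 28 + 7 = 35. At day 35, four weekly steps (days 7, 14, 21 and 28) precede it. From an entry dose of 4mg/kg/day, all four increases would then be off-schedule. The nominal counts are therefore not upper bounds.

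**Interval between required forms.** For an EP0060 initiator, Visit 1 to Visit 2 is 28 days nominal, 21 to 35 with the window. Visit 2 to Visit 3 is 28 days nominal and at most (56 + 7) − (28 − 7) = 42. For a direct enrollee in titration it is about 7 days, with at least 5 days at each dose. For ideation that begins just after Visit 1, the extra wait for a required form is about 28 − 7 = 21 days, or 35 − 7 = 28 at the late end of the window.

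**The case against.** The strongest reply is that nothing here is contradictory. Section 5.18 and both table footnotes state one AE-only rule, and it applies to every subject after Visit 1. It also looks deliberate: the superseded Amendment 3 text listed the C-SSRS at Unscheduled Visits without that condition. Scheduled visits later in the study are further apart than four weeks and dose increases remain allowed, so a gap that spans dose steps is not peculiar to EP0060 initiators. Exclusion criterion 3 already keeps out children aged 6 or over with a lifetime suicide attempt, or with Question 4 or 5 ideation in the past 6 months. Titration is optional, the scheme is only recommended, and the EP0060 protocol is not at hand.

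Much of this stands. The AE-only rule for later increases is a general design choice and is not challenged here. What remains is narrower: for initial titration the protocol pairs each step with a C-SSRS in one group and not in another group referred to the same steps. Exclusion criterion 3 lowers the risk at entry but does not detect ideation that arises afterwards.

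Three stronger readings should be resisted.
- A reader might infer that these children go unassessed between Weeks 0 and 4. They do not: the Week 4 Since Last Visit form covers the interval. Each Unscheduled Visit includes a mental-status check (Sections 5.18 and 8.4.2.2) and AE reporting, and there is a telephone contact at Week 2. An AE-driven visit triggers the C-SSRS, and the investigator may add it at any time.
- A reader might infer that LCM dose steps provoke suicidal ideation. The protocol does not say so, and its AEs of special interest (Section 8.2.2) do not include it.
- A reader might take the step counts as worst cases. They depend on an unstated entry dose, the week of the first increase and the visit window.

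**Conclusion.** The point holds as a possible delay in detection, confined to children aged 6 or over who initiated LCM in EP0060 and are raised between scheduled visits during initial titration in SP848. Their required C-SSRS interval is about four times that of direct enrollees on the same steps (28/7 = 4).

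The conclusion rests on weekly increases actually being made after Visit 1, and on entry below the maximum dose. Sections 1 and 12.2 cap EP0060 entrants at about 100. How many of them initiated LCM there, are aged 6 or over and are up-titrated between visits is not given. The existing safeguards reduce the consequence, but none requires the structured questions at a dose step without an AE. The change is worth making because the outcome is serious and the remedy is small. It is not a flaw in the study's analysis.

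**What to change.** Amend Section 5.18 and Table 16-1 footnote q, and Table 16-2 footnote o for consistency. The added rule: at age 6 or over, the Since Last Visit C-SSRS is also required at any Unscheduled Visit held to increase the LCM dose of an EP0060 initiator during initial titration under Section 4.4.1.2. The form would then accompany every titration step, at about 7-day intervals, as for direct enrollees.

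Do not extend the full Titration Visit list to these children. Titration Visit 4 includes endocrinology and urinalysis, which Visit 2 does not. Visit 1, doses, titration rate and number of visits stay as they are.

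The cost is one section and two footnotes to reword, and one short questionnaire at a few visits that are already required (four on nominal dates from the lowest entry dose with a first increase at Week 1), for a subset of at most about 100 subjects.

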#### 4.4.1.2 Subjects enrolling directly into SP848

Beginning with Protocol Amendment 4, at selected sites, up to approximately 100 eligible pediatric subjects  $\geq 4$  years to  $\leq 17$  years of age who have not previously participated in a LCM clinical study will be permitted to enroll directly into SP848. Beginning with local Protocol Amendment 5.2 for sites in Japan, approximately 46 eligible pediatric subjects  $\geq 4$  years to  $\leq 17$  years of age with partial-onset seizures who have not previously received LCM will directly enroll at approximately 9 sites in Japan. Beginning with local Protocol Amendment 5.4 for sites in China, approximately 60 additional eligible pediatric subjects with partial-onset seizures aged  $\geq 4$  years to  $\leq 17$  years, who have not previously participated in a LCM clinical study, will enroll directly into SP848. After Screening, eligible subjects will initiate treatment with LCM (oral solution or tablet, as chosen by the investigator and subject/caregiver), and the LCM dose will be titrated to a level to optimize tolerability and seizure control.

At the first Titration Visit (TV) (see [Section 5.2](#)), subjects who have enrolled directly into SP848 will receive a single dose of LCM (1mg/kg [oral solution] or 50mg [tablet]) during the clinic visit. Over the following days, subjects will be administered LCM 1mg/kg bid (oral solution) or LCM 50mg bid (tablet), and will begin titrating in weekly increments of 2mg/kg/day (oral solution) or 100mg/day (tablet) up to a level to optimize tolerability and seizure control (not to exceed 12mg/kg/day [or 600mg/day based on body weight, whichever is lower]). Subjects must be on each LCM dose for at least 5 days before titrating up to the next dose.

A total of up to 6 Titration Visits may be required (eg, for a subject whose dose is titrated to the maximum permitted dose of LCM 12mg/kg/day). However, based on tolerability and seizure control, a subject's LCM dose may be titrated to a lower dose level; in such a case, fewer than 6 Titration Visits would be required.

The following table summarizes the recommended titration steps for the oral solution and tablet formulations:

